Copies of all of the subject case report forms will be made and supplied to Erchonia Corporation who will maintain these copies in a separate clinical study file that is kept in a locked filing cabinet at their premise. The original records will be maintained at the respective test sites.

Subjects' identities will be kept confidential by assigning each subject a subject ID upon acceptance into the study. The subject ID will comprise the investigator's first and last name initials followed by a three-digit number determined according to the subject's order of entry into the study. The first test site will be assigned a range of numbers from 001 to 100. The second test site will be assigned a range of numbers from 101 to 200. For example, the eighth subject to be enrolled at the first test site under PI [name] would have a subject ID of JB008. Neither the study Sponsor, Monitor, biostatistician, Independent Blinded Evaluators, nor any other pertinent party will receive any additional identifying information about a subject and will therefore have no way of linking a Subject ID to a particular subject and his or her study results.

STATISTICAL ANALYSIS PLAN

STUDY POPULATIONS

The following two study populations will be evaluated:

1. Intent-to-Treat (ITT) Population

Primary analysis of efficacy will be according to the intent to treat (mITT) analysis, including all consented and enrolled subjects.

2. Per Protocol Population

Secondary analysis of efficacy to confirm the findings of the primary analysis will be conducted on the Per Protocol population, comprised of all subjects who completed the study per protocol inclusive of all assessment visits and activities and the full 4-week, 8-treatment administration protocol.

3. Handling of Missing Data

Missing data values will be imputed using regression analysis imputation methodology under the assumption of the data missing at random (MAR), provided that the assumption of the data being MAR can be supported as has been found through prior Erchonia studies and demonstrated through the following means, the first two of which are already established by the study design:

1. As there is no placebo group in this clinical study design, subjects are aware that they are receiving active study treatments, and therefore, subject lost to follow up cannot be attributed to potential study unblinding.

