2. The primary outcome assessment is a binary response responder rate format determined by Independent Blinded Evaluators that is therefore independent of individual subject variables.
3. Comparison of demographics for the group of subjects with missing data to the entire subject ITT group will be performed to demonstrate comparability.
4. Comparison of the primary outcome assessment for the group of subjects with missing data to the entire subject ITT group will be performed to demonstrate comparability.

Given that the assumption of the data being MAR is supported, the missing data will be imputed using the regression imputation methodology with known variables approach wherein the regression equation is employed to calculate the marginal or conditional average for each individual subject's missing value based on the known Baseline value of the missing variable value being imputed for that subject if available or if not available, on the known Baseline value for other subject(s) with comparable demographic profiles.

DEMOGRAPHICS

The following subject demographics collected at the Pre-Treatment assessment visit will be analyzed descriptively as means, standard deviations, medians, and range (minimum, maximum) for continuous data and as number (N) and percentages(%) of the total sample for categorical data and presented in table format, as applicable for the ITT subject population.

- Gender
- Age

- Ethnicity
- Body Mass Index (BMI): weight (kg), Height (inches / meters).

BASELINE SKINFOLD MEASUREMENTS

Baseline skinfold measurements (mm) and submental skinfold thickness (mm) measurements will be presented descriptively in table format as means, standard deviations, medians, and range (minimum, maximum) for the ITT subject population.

BASELINE CONCOMITANT MEDICATION USE

Recorded baseline concomitant medication use will be presented in table format as number (N) and percentage (%) of totals and reported as individual medications and further groups by indication for use for the ITT subject population.

PRIMARY EFFICACY OUTCOME ANALYSIS

The primary goal of this study is to determine if the treatment effect of the Erchonia© CFL can affect the appearance of visible fat bulges in the submental area.

PRIMARY STUDY SUCCESS EVALUATION CRITERIA

The primary efficacy outcome for this clinical study is established as the proportion of accurately identified subject pre- and post-treatment photographs by at least two of the three Blinded Independent Evaluators.

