3. If the calculated responder rate is less than 80% ($< 80\%$), it will be concluded that primary efficacy success has not been demonstrated.

SECONDARY EVALUATIONS The secondary efficacy outcomes of submental skinfold and submental skinfold thickness, and subject satisfaction with treatment outcome will be assessed for each of the ITT and Per Protocol analysis populations, as applicable. As these secondary outcomes are provided as supportive evidence for the primary efficacy outcome only and the Sponsor **does not intend to seek clearance for any claims based on findings of these secondary efficacy outcomes**, the findings will be presented descriptively only as means, standard deviations, medians, and ranges for the continuous data and as number (N) and percentage (%) of the total for categorical data and will be presented in table and chart format, as applicable. Statistical analysis of change will not be performed.

- Submental skinfold and submental skinfold thickness measurements (mm) data will be recorded at each of the Pre-Treatment (Baseline), Week 4 (Treatment End), and Week 16 (12 Weeks Post-Treatment End) visits.
- Subject satisfaction with study outcome ratings will be recorded at each of the Week 4 (Treatment End) and Week 16 (12 Weeks Post-Treatment End) visits.

'Positive' subject satisfaction with treatment outcome response is predefined as the sum of 'Very Satisfied' and 'Somewhat Satisfied' responses.

- Additionally, comparison of the mean, standard deviation, median, and range of Body Mass Index (BMI) recording at each of Pre-Treatment (Baseline), Week 4 (Treatment End), and Week 16 (12 Weeks Post-Treatment End) visits will be compared descriptively to confirm that changes in body BMI did not contribute to the study outcome.

SAFETY ANALYSES

Safety analyses will be based on all subjects who signed informed consent and were enrolled in the study.

Safety will be assessed by evaluating observed and/or reported adverse events.

INFORMED CONSENT

- Informed consent will be an agreement between the individual investigator and each subject, having the capacity to understand and make an informed decision. Consent will be obtained prior to each potential subject's participation in this study.
- Each subject participating in this study will be made aware of the fact that his or her participation involves research and the intent of the research, the expected duration of participation and a description of the procedures that will be followed.

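### Minor: missing Week 16 skinfold and BMI values are filled with one regression average from Baseline alone, which understates the SDs in the ITT descriptive tables and leaves the Week 4 reading unused

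*Combined protocol and SAP*

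**What the plan says.** The Handling of Missing Data section of the SAP imputes missing values by regression, provided that missing at random (MAR) is judged to be supported. The fill is a single number: "the regression equation is employed to calculate the marginal or conditional average for each individual" subject with a gap. The only predictor named is the subject's own starting value: "based on the known Baseline value of the missing variable value being imputed for that subject if available". If that is absent, the fill rests "on the known Baseline value for other subject(s) with comparable demographic profiles". The section describes no residual draw, multiple imputation or sensitivity analysis, and it does not name Week 4 as a predictor.

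Week 4 data will exist. For skinfold, Secondary Evaluations states that "data will be recorded at each of the Pre-Treatment (Baseline), Week 4 (Treatment End), and Week 16", and the Week 4 Evaluation section also lists BMI. Secondary Evaluations fixes the output for both the ITT and Per Protocol populations: "the findings will be presented descriptively only as means, standard deviations, medians, and ranges for the continuous data". It plans no statistical analysis of change. BMI is summarised at the three visits by mean, SD, median and range, to check that body weight did not drive the result.

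**The concern.** This point is confined to skinfold and BMI, the continuous outcomes to which the rule can be applied as written.

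- **Spread.** Values on a regression line vary less than real values. SD and range are two of the four summaries planned for these outcomes, so the completed data understate something the tables are meant to show.
- **Week 4.** A subject lost between Week 4 and Week 16 has one post-treatment reading, and the rule does not use it. MAR lets dropout depend on anything observed, including Week 4. Imputing from Baseline alone is valid only if dropout is unrelated to Week 4 once Baseline is known, which is a stronger assumption than the one the SAP states. None of its four supporting arguments looks at Week 4 skinfold or BMI. A subject with no reduction at Week 4 who then leaves is given the Week 16 value predicted from those who stayed. Likewise, the Week 16 BMI check takes no account of a weight change already seen at Week 4.

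**Working it through.** **Inputs from the documents.** Rationale for Sample Size gives 30 evaluable subjects, 15% attrition and 35 enrolled. The enrolment figure reproduces: 30 × 1.15 = 34.5, rounded up to 35 (dividing instead, 30/0.85 = 35.3, gives 36). So about 35 − 30 = 5 subjects lack Week 16 data.

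**Assumed inputs.** The documents give no SDs or between-visit correlations. I assume equal SDs at Baseline and Week 16, a Baseline-Week 16 correlation r of 0.5 to 0.95, and, for the formulas, dropout unrelated to the values.

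**Week 16 SD.** Observed values have variance σ². Values on the regression line have variance r²σ². The ratio of the completed-data SD to the full-data SD is √((30 + 5r²)/35). If the marginal mean is inserted, it is √(30/35).

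**SD of change from Baseline.** Observed change has variance 2(1 − r)σ² and imputed change has (1 − r)²σ². The ratio simplifies to √((60 + 5(1 − r))/70).

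| r | Week 16 SD ratio | SD-of-change ratio |
|---|---|---|
| 0.5 | √(31.25/35) = 0.945 | √(62.5/70) = 0.945 |
| 0.7 | √(32.45/35) = 0.963 | √(61.5/70) = 0.937 |
| 0.85 | √(33.61/35) = 0.980 | √(60.75/70) = 0.932 |
| 0.95 | √(34.51/35) = 0.993 | √(60.25/70) = 0.928 |
| marginal mean | √(30/35) = 0.926 | not computed |

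A simulation (n = 35, 5 imputed, 8,000 replicates, trivariate normal) gave Week 16 SD ratios of 0.943, 0.961 and 0.993 at r = 0.5, 0.7 and 0.95, close to the formula.

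**Range.** In the same simulation the mean range after Baseline-only imputation was 0.968, 0.974 and 0.993 of the full-data range at r = 0.5, 0.7 and 0.95. Among the 30 observed subjects alone it was 0.968, 0.970 and 0.970. Imputation restores little of the lost range unless r is high, but it never narrows the observed range.

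**What Week 4 adds.** Assume correlations of 0.7 (Baseline-Week 16), 0.85 (Week 4-Week 16) and 0.8 (Baseline-Week 4). Baseline alone explains 0.7² = 49% of the Week 16 variance. Both visits explain (0.49 + 0.7225 − 2 × 0.7 × 0.85 × 0.8)/(1 − 0.64) = 0.2605/0.36 = 72%. The simulated error of the imputed values falls from 0.74 to 0.56 SD, and the SD ratio rises from 0.961 to 0.980. Some shrinkage remains because the fill is still an average; a residual draw is needed to remove it.

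**Bias in the mean.** In a further simulation, the 5 dropouts were those with the largest sum of standardised Week 4 value and unit-variance noise, so subjects with larger Week 4 skinfolds tended to leave. Baseline-only imputation put the Week 16 mean 0.076 SD too low (correlations 0.5, 0.7, 0.6 in the same order) or 0.058 SD too low (0.7, 0.85, 0.8). A low mean overstates the reduction. Adding Week 4 brought the bias to 0.000 in both cases. With dropout unrelated to the values, the Baseline-only bias was at most 0.001 SD.

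**The case against.** The strongest reply is that this hardly matters. The outcomes are supportive and descriptive, the sponsor seeks no clearance claim from them, and about five values are filled. The Per Protocol tables, limited to subjects with all assessment visits, will stand beside the ITT tables and let a reader see roughly what imputation did. All of that stands, and it is why the point is minor. It does not make the rule sound: the ITT tables are still reported, and Per Protocol is not an observed-case table by visit, because it drops the Week 4 data of anyone who later left.

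Several stronger readings are tempting, and the documents do not support them:

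- **Standard errors.** A reader might infer that standard errors computed at n = 35 would be falsely small. No standard error, interval or test is planned for these outcomes.
- **Inflated mean reduction.** A reader might infer a large inflation: if 30 completers lost 2.0 mm and 5 dropouts nothing, the true mean is (30 × 2.0 + 5 × 0)/35 = 1.71 mm, not about 2.0. That is a constructed worst case. An observed-value table would also show 2.0, and Week 4 helps only if those subjects reached Week 4 and the reading there foretells Week 16. Mean bias is conditional, not certain.
- **Replaced Week 4 values.** A reader might infer that the rule replaces an observed Week 4 BMI. It fills only missing values, and the Week 4 result stays in its own row.
- **Narrower range.** A reader might infer that imputation narrows the range. It cannot fall below that of the observed cases.
- **BMI affected as much as skinfold.** Subjects agree to keep weight within 5%, so a correlation near 0.95 is plausible and the loss of SD in BMI is then about 1%.

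**Conclusion.** The point holds as a minor one, limited to the ITT descriptive tables of skinfold and BMI and to the case where MAR is accepted and the imputation is carried out. With about 5 of 35 values filled, the Week 16 SD is about 2-6% too low for correlations of 0.5-0.85, about 1% at 0.95, and 7% with the marginal mean. The SD of change, which Secondary Evaluations does not list, would be 6-7% too low if reported. For subjects who have a Week 4 reading, leaving it out biases the Week 16 mean only if dropout relates to Week 4 beyond Baseline; under the dependence assumed above, the bias is about 0.06-0.08 SD. All these sizes rest on assumed correlations and on the plan's own attrition. The Week 16 responder decision does not depend on these tables.

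**What to change.** For skinfold and BMI, tabulate observed values with n at Baseline, Week 4 and Week 16. For the ITT version, replace the single-average fill with multiple imputation that includes residual draws and uses Baseline and, where observed, Week 4. State how SD, median and range will be summarised over the imputations, since the range in particular has no single natural combined value. A repeated-measures model is not a substitute, because it gives model means and not the SDs, medians and ranges the SAP reports.

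The cost is a few lines of SAP text, a little more analysis work and slightly larger reported SDs. No new data are needed.

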In consideration of the primary efficacy outcome assessment, a clinically important outcome is pre-established as at least 2 of the 3 Independent Blinded Evaluators correctly identifying a subject's Pre-Treatment and Post-Treatment (study Endpoint of Week 16 – 12 Weeks Post-Treatment End) photographic images of the submental region, with study success defined as a Responder Rate of 80% or greater.

Consequently, the planned sample size to provide sufficient power for a statistical comparison of the proportion of treatment responders (P) versus a reasonable cutoff (P0) is based on a power calculation utilizing the (one proportion) binomial exact test based on the following assumptions.

- $H_0: P \leq P_0$ versus $H_a: P > P_0$
- Type I error rate: $\alpha = 0.025$
- Power = 90%
- Population proportion under the null hypothesis: $P_0 = 0.80$
- Population proportion under the alternative hypothesis: $P = 0.50$
- Total N = 30 study participants

To account for a potential 15% subject attrition rate, a total of 35 subjects will be enrolled.

Recruitment

Subjects will be recruited from among:

- (i) The test site's pool of existing and new clients
- (ii) Subjects who respond to the recruitment materials found in **Appendix C**.

Compensation

A subject will not be offered money or any other form of compensation to participate in the study; however, he or she will also not be charged for the cost of the study procedures with the Erchonia® CFL or for the cost of any other directly-related evaluations or measurements that occur as part of his or her participation in the study.

STUDY PROCEDURE

STUDY TEST BATTERY

The following is a list of the study measurement tools to be used in this study. For each study phase, the precise tools from this list that will be employed will be specified.

BODY MASS INDEX (BMI): BMI is calculated as the ratio of the subject's weight in kilograms (or pounds) to the square of the subject's height in meters (or feet).

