
In consideration of this primary efficacy outcome assessment, a clinically important outcome is defined as at least 2 of the 3 Independent Blinded Evaluators (i.e., 2 out of 3, or 3 out of 3) correctly identifying the order of a subject's Pre-Treatment (Baseline) and Week 16 (Endpoint) 12 Weeks Post-Final Treatment photograph for 80% or more of subjects.

This clinically important minimum upper limit criteria of 80% was selected to be identical to the respective primary efficacy endpoint assessment parameters from the clinical studies for the ZELTIQ CoolSculpting System (K151179), and SculpSure (K171992) whose outcomes successfully supported FDA clearances for the same indication as intended to be supported by the outcome of the current clinical study protocol.

HYPOTHESES

The null and alternative hypotheses for the Primary Efficacy Endpoint are the following:

Null Hypotheses: The overall responder rate will be less than 80%.

$$H_0: \mu A < 80\%$$

Alternative Hypothesis: The overall responder rate will be 80% or greater.

$$H_0: \mu A \geq 80\%$$

PRIMARY EFFICACY OUTCOME ANALYSIS POPULATION

Determination of primary efficacy outcome success will be according to analysis of the outcome

for the subject ITT population as the primary analysis population. Primary efficacy outcome success will also be evaluated for the study Per Protocol population as a secondary analysis to provide support for and confirm the outcome of the primary analysis performed on the ITT subject population.

PRIMARY EFFICACY OUTCOME STATISTICAL EVALUATION

Primary study efficacy will be evaluated at Week 16, 12 Weeks Post-Final Treatment administration relative to Baseline (Pre-Treatment).

Primary efficacy outcome success will be evaluated via Responder Rate Analysis, wherein:

- (i) An individual subject is defined as a Study Responder if at least 2 of the 3 Independent Blinded Evaluators correctly identify the subject's post-treatment photograph, and
- (ii) Overall study success is defined as a minimum responder rate of 80%.

To determine primary efficacy outcome success, the following process will be followed:

1. The percentage of individual Study Responders will be calculated to determine the responder rate.
2. If the calculated responder rate is 80% or greater ($\geq 80\%$), it will be concluded that primary efficacy success has been demonstrated.

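### The SAP's success rule (observed responder rate of at least 80%) is not the exact binomial test the trial was sized on, so the stated 2.5% alpha and 90% power do not describe it

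*Combined protocol and SAP*

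**What the plan says.** **Sizing.** The protocol section Rationale for Sample Size bases N on "a power calculation utilizing the (one proportion) binomial exact test". It lists alpha 0.025, power 90%, a null proportion of 0.80, an alternative proportion of 0.50 and N = 30, raised to 35 for 15% attrition. The hypotheses there are one-sided and upward (null P ≤ P0, alternative P > P0), so the printed alternative of 0.50 lies on the wrong side of the printed null.

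**Hypotheses in the SAP.** The Hypotheses section reads: "Null Hypotheses: The overall responder rate will be less than 80" per cent. The alternative is a rate of 80% or more. Both lines carry the symbol H0.

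**Decision rule in the SAP.** Primary Efficacy Outcome Statistical Evaluation calculates the percentage of responders and applies two rules. "If the calculated responder rate is 80% or greater", success has been demonstrated. "If the calculated responder rate is less than 80" per cent, it has not. No test, alpha, p-value or confidence interval is named for the primary endpoint. Under Secondary Evaluations, only the secondary outcomes are declared to be descriptive.

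**The concern.** A power statement belongs to a particular decision rule. Here the power was computed for an exact test, but the trial is decided by comparing a point estimate with 80%. Because the documents give two incompatible nulls, the harm depends on which one is meant:

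- **Reading (a): the two printed proportions were exchanged, so the null is 0.50 and the alternative 0.80.** The written rule is then stricter than the powered test. The sponsor faces a much larger chance of a failed trial than the protocol states.
- **Reading (b): the null is a rate below 80%, as in the SAP.** A declared success then implies that the true rate is at least 80%, with no control of the chance that this is wrong.

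This is the only primary decision in the trial, and its result is intended to support a 510(k) submission.

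**Working it through.** **Inputs.** From Rationale for Sample Size: alpha 0.025 one-sided, power 0.90, the proportions 0.80 and 0.50, N = 30, and 35 enrolled. From the SAP: success at an observed rate ≥ 80%, which is 24/30 or 28/35 (0.8 × 30 = 24; 0.8 × 35 = 28). The primary analysis is on all enrolled subjects with imputation, so both sizes are shown. True rates other than 0.80 and 0.50 are assumptions used to show the range.

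**Formula.** For X ~ Binomial(n, p), P(X ≥ r) = Σ from k = r to n of C(n,k) p^k (1−p)^(n−k). The critical value is the smallest r with P(X ≥ r | P0) ≤ 0.025.

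**Step 1. Reproduce the plan's N = 30.**

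| Interpretation | Rejects at | Size | Power |
|---|---|---|---|
| As printed: P0 = 0.80, P = 0.50, upper tail | ≥ 29/30 | 0.0105 | about 3 × 10⁻⁸ |
| Proportions exchanged: P0 = 0.50, P = 0.80, upper tail | ≥ 21/30 | 0.0214 | 0.939 |
| Printed proportions, tail reversed | ≤ 18/30 | 0.0095 | 0.8998 |

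The printed inputs do not give 90%. Exchanging the proportions or reversing the tail does, but reversing the tail would test for a rate *below* 80%, opposite to the printed alternative. The exchange is the sensible reading. It also gives 0.50 a meaning: if three evaluators guess independently between two photographs, P(at least 2 of 3 correct) = 3 × 0.5³ + 0.5³ = 0.50. None of the three is the rule in the SAP.

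**Step 2. Operating characteristics of the written rule.**

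| True rate | P(X ≥ 24), n = 30 | P(X ≥ 28), n = 35 |
|---|---|---|
| 0.50 | 0.0007 | 0.0003 |
| 0.70 | 0.160 | 0.133 |
| 0.75 | 0.348 | 0.322 |
| 0.79 | 0.553 | 0.541 |
| 0.80 | 0.607 | 0.599 |

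Solving P(success) = 0.90 gives a true rate of 0.865 (n = 30) or 0.862 (n = 35). For n = 31 to 34, 80% is not a whole number of subjects and the rule rounds up. Success at a true 0.80 is then lower: 0.571, 0.535, 0.500 and 0.466.

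**Step 3. Reading (a).** The powered test rejects at 21/30 (power 0.939 at 0.80) or 24/35 (size 0.0205, power 0.966). The written rule needs 24/30 or 28/35. At a true 0.80, the probability of passing the test but being declared a failure is:

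- n = 30: P(21 ≤ X ≤ 23) = 0.939 − 0.607 = 0.332
- n = 35: P(24 ≤ X ≤ 27) = 0.966 − 0.599 = 0.366 (from unrounded values)

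**Step 4. Reading (b).** A rate of exactly 80% belongs to the SAP's alternative, so about 0.60 is the value that the false-success rate approaches as the true rate nears 80% from below. An observed 28/35 has a one-sided exact p-value of 0.60 against 80% and an exact (Clopper-Pearson) 95% interval of 63.1% to 91.6%. For 24/30 the interval is 61.4% to 92.3%.

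An exact test of the 80% null at 0.025 would need ≥ 29/30 (size 0.0105) or ≥ 33/35 (size 0.0190). Its power at a true 0.90 is 0.184 or 0.306. It reaches 90% power only at a true 0.982 or 0.968.

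**The case against.** The 80% threshold is deliberate. It appears consistently in Expected Results, Rationale for Sample Size and the SAP, and the SAP says it was chosen to match the endpoint used for two cleared devices. A pre-specified performance goal on the observed rate is a legitimate criterion. Under reading (a) it is also stricter than the powered test: its type I error against 0.50 is below 0.1%, so no false claim against chance is at risk. Any result that meets 80% would also pass the test against 0.50, so adding the test changes no decision while the goal stays mandatory. It can also be said that the rationale does name a test, so the test is not carried into the SAP rather than ruled out, and that the SAP concludes only that efficacy success was shown, not that the true rate is at least 80%.

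Much of this stands. The goal may be kept, the rule is not lax against chance, and the exact description is that the SAP does not specify the test. It does not rescue the stated figures, however. The strictness of the rule is the reason its power falls to about 60%. The SAP also writes formal hypotheses about 80% and then decides between them on a point estimate, so the inference under reading (b) is one the text invites. Nothing elsewhere in the documents settles which null is meant.

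**Conclusion.** The concern holds and should be corrected before the evaluators' results are known. The stated alpha of 0.025 and power of 90% do not describe the rule that decides the trial, whichever null is intended.

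- **Null 0.50:** power at the design alternative of 80% is about 60% (47% to 57% if 31 to 34 subjects are analysed). At that rate there is a 33% to 37% chance of failing the trial while passing the test it was sized for.
- **Null below 80%:** false success is 54% to 55% at a true 79% and 32% to 35% at a true 75%, against a stated 2.5%.

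The arithmetic assumes independent subjects with a common responder probability and a denominator of 30 to 35. Reading (a) is preferred because it fits the stated N and the upward alternative, but that is an inference. The sponsor must say which null it meant.

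**What to change.** State one hypothesis pair, identically, in Rationale for Sample Size and in the SAP, and name the primary test in the SAP. The choice of null is the sponsor's.

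**Option A (fits the stated N; recommended).**
- Exchange the two proportions in the rationale, and write H0: P ≤ 0.50 against Ha: P > 0.50 in both places, correcting the duplicated H0 label.
- Specify the one-sided exact binomial test at 0.025 and report the exact 95% confidence interval.
- Require both rejection of H0 and an observed rate of at least 80%. If the goal were made optional, the bar would drop to 21/30 (70%) or 24/35 (69%).
- Give the power of the test (0.939 at N = 30, 0.966 at N = 35, true rate 80%) separately from the probability of meeting the goal (about 60% at a true 80%, and 90% only at about 86% to 87%). State the true rate the sponsor expects.
- Limit the conclusion to identification better than chance with an observed rate that met the goal.

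The cost is SAP wording and one test, with no extra subjects. The price is a less favourable power statement for the 80% goal and a narrower conclusion.

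**Option B.** Keep the 80% null and test it exactly (≥ 29/30 or ≥ 33/35), then replace the power statement and N. At an assumed true rate of 90%, power first reaches 90% at N = 137 and stays there from N = 149. At an assumed 95% the figures are 48 and 55. This needs more subjects unless the true rate is about 97% to 98%.
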